## **1- NAME OF THE PROJECT**

**“The Effect of Central Sensitization on the Treatment Success of Ultrasound-Guided Caudal Epidural Steroid Injection in Radicular Pain in Patients with Failed Back Surgery Syndrome”**

## **2-QUALITY OF THE RESEARCH**

Non-Pharmaceutical Prospective Observational Clinical Trial

## **3- IN MULTI-CENTER RESEARCH, CENTERS OUTSIDE THE INSTITUTION :**

The research is not multicenter.

## **9-JUSTIFICATION / PURPOSE OF THE STUDY :**

Low back pain is a very common clinical entity that has a tremendous social, financial and psychological impact on the patient's life. It is a worldwide problem, with a global incidence of 9.4%, and causes more disability than any other condition in the world. The percentage of adults who experience chronic low back pain throughout their lives varies between 51% and 84% (1). As the population ages, the incidence of surgery for low back pain increases dramatically; The number of lumbar fusions increased by as much as 170% from 1998 to 2008 (2). Failed back surgery syndrome (FBSS) has been reported to affect 10 to 40% of patients following spine surgery, but estimating the incidence of FBSS is difficult due to the broad scope of its definition and heterogeneous etiology ( 3 ). Failed back surgery syndrome (FBSS) is defined by the International Association for the Study of Pain as "lumbar spinal pain of unknown origin that persists despite surgical intervention or occurs after surgical intervention for pain in the same topographic area" (4). Pain may occur after surgery, as surgery may aggravate or fail to adequately heal existing pain. Patients with FBSS have long-standing chronic low back pain, with or without radicular symptoms, and have had one or more surgical interventions that do not treat the pain. Its etiology is complex and it is a condition with many factors that predispose patients to chronic pain. Epidural fibrosis, perineural scars, acquired stenosis, recurrent disc herniation or pain in the sacroiliac/facet joints are thought to play a role in the etiology of FBSS. Pain in the leg likely indicates nerve compression resulting from stenosis, epidural fibrosis, or disc herniation, while lower back pain is more common in facet joint arthropathy, sacroiliac joint problems, or myofascial etiologies . For the failed back surgery syndrome patient, physical examination is generally not useful

in determining a specific pain etiology, but may reveal several suggestive findings. Symptoms resulting from spinal stenosis are usually exacerbated by spinal extension and relieved by flexion. On the other hand, pain from disc herniation causes a positive straight leg raise test. Loss of strength or sensation in the lower extremities can help figure out which nerve roots are affected. Other tests may be used to elucidate the etiology of failed back surgery syndrome and differentiate it from other causes of low back pain. Erythrocyte sedimentation rate and C-reactive protein can be used to evaluate possible infection, especially in patients with constitutional symptoms or a predisposition to infection. Diagnostic nerve blocks can diagnose specific etiologies of FBSS, such as facet joint arthropathy (medial branch blocks), sacroiliac joint pain (lateral branch blocks and intra-articular injection), and foraminal stenosis (transforaminal epidural and selective single-level blocks) and roots associated with the patient's symptoms. can define. MRI with and without gadolinium contrast remains the gold standard imaging modality for failed back surgery syndrome due to its excellent ability to detect soft tissue abnormalities such as epidural fibrosis and disc herniation. Contrast is especially indicated in patients with a history of disc herniation surgery. An international panel of spine surgeons, neurosurgeons and pain specialists with a special interest in FBSS established the Chronic Low Back and Leg Pain (CBLP) network to address challenges and barriers in the clinical management of FBSS patients by creating a common interdisciplinary structure. The definition of FBSS proposed by the CBLP network is based on the prediction that no further spine surgery is required after an appropriate somatic, radiological and psychosocial evaluation (5). The key elements for the definition of FBSS can be summarized in 4 aspects:

1. There is back and/or leg pain that has persisted for at least 6 months after the most recent spine surgery.
2. The patient has undergone a comprehensive clinical and radiological evaluation
3. There is no clear surgical target compatible with the symptoms revealed on clinical examination and imaging
4. There is an interdisciplinary consensus that additional surgical intervention (decompression and/or fusion) is not appropriate

Despite its adverse effects on patients and its relative prevalence in the population undergoing spine surgery, there are few high-quality randomized trials investigating the treatment of FBSS. (6). Treatments for FBSS are generally divided into conservative (physical therapy or drug therapy) and aggressive (interventional or surgical) management. Conservative treatment should always be the first choice before invasive techniques in patients who do not have an indication for urgent surgery (7). Various studies have shown that caudal ESI (CESI) is an effective method in patients with FBSS who do not respond to conservative pain-relieving treatments (8). Çelenlioğlu A. et al. In a prospective randomized study comparing the treatment success of TFESI and CESI in patients who developed FBSS after single-level discectomy, both CESI and TFESI (transforaminal epidural steroid injection) were

found to be effective and safe in treatment. CESI has been shown to be the safest and simplest ESI with a low rate of complications, including dural puncture and other side effects, compared to other injection methods (9). Yoon et al. (10) reported the success rate of US-guided caudal blockade as 94% (11). In a study conducted by Akkaya et al. (12), comparing ultrasound and fluoroscopy-guided caudal epidural steroid injection (CESI) in patients with FBSS, a decrease in both pain and ODI scores was achieved in both groups at 3-month follow-up, and CESI was found to be effective in the treatment of FBSS. has been reported. In a prospective randomized controlled study comparing the treatment success of caudal epidural steroid injection guided by ultrasonography (USG) and fluoroscopy in postlaminectomy patients, no difference was found in terms of complications between the two groups, while patients in the fluoroscopy group felt more pain during the intervention than patients in the USG group. Despite accurate needle localization and drug injection under fluoroscopic guidance, radiation is still a serious risk for both the patient and the interventionalist. The use of USG in caudal epidural injections protects against radiation exposure and is a safe and rapid method to locate the sacral hiatus and guide the needle (9). Color Doppler USG can visualize intravenous injections. Tsui et al. (13) reported that the color Doppler feature of US can confirm whether the injected drug diffuses into the caudal area. Injection of fluid into the epidural space causes turbulent flow, which appears as a burst of color, whereas intrathecal injection shows the absence of color flow Doppler signal. Although the exact pathophysiological process of FBSS remains unclear, increasing evidence suggests that the symptoms of diffuse pain distribution, hyperalgesia, and disproportionate pain intensity, which are also common in other chronic pain-related diseases (e.g., fibromyalgia, tension-type headache, and nonspecific chronic low back pain), are a potential pain disorder. predicts that central sensitization may develop (14). The International Association for the Study of Pain (IASP) defined CS in 2011 as "the increased response of nociceptive neurons in the central nervous system to normal or subthreshold afferent input." Anxiety about pain, limitation of daily activities, quality of life and related stress lead to depression over time, thus beginning a vicious "pain-anxiety-depression" cycle. Altered central pain modulation may be involved in the pathogenesis of FBSS. Unfortunately, only a few studies have investigated the presence of central sensitization in patients with FBSS, although it may guide treatment. Central amplification of pain may contribute to both chronic low back pain intensity and disability in FBSS patients. Therefore, targeted treatments should take into account functional changes in the central nervous system of FBSS patients, and treatment modalities that can attenuate central sensitization (e.g., cognitive targeted exercise therapy, pharmacotherapy, spinal cord stimulation) may be useful in the treatment of FBSS. Our aim is to reveal the relationship between FBSS and central sensitization proportionally, to prevent the formation of a vicious circle of chronic pain with early detection and treatment, keeping in mind that central sensitization may develop in postspinal surgery patients with ongoing pain, and also to prevent the formation of a vicious cycle of chronic pain with USG-guided caudal epidural steroid injection, as there is no radiation exposure and it is advantageous and beneficial. Since it is a reliable

method, we aim to determine its effectiveness in patients with FBSS. To our knowledge, such a study has not been reported before in the literature. We hope to contribute to the literature.

## **10-APPROACHES AND METHODS TO BE APPLIED :**

Among the patients who applied to Marmara University Pendik Training and Research Hospital, Physical Medicine and Rehabilitation and Algology outpatient clinics with complaints of low back pain, were diagnosed with FBSS by Algology after clinical, physical examination and radiological imaging and were planned for caudal epidural steroid injection, which is a treatment option applied in routine clinical practice. Those who meet the exclusion criteria will be included in the study after detailed information about the research is given and their verbal and written consent is obtained. These patients will not undergo additional treatment, any imaging methods or laboratory tests. Patients diagnosed with or in contact with Covid-19 will not be processed until the quarantine period expires. Patients will be reminded to comply with the mask and distance rules in the waiting area before the procedure and in the observation area after the procedure, not to touch any surfaces in the hospital unless necessary, and to frequently disinfect their hands. During the evaluations, the patient and the physician; will comply with mask, distance and hand hygiene rules. After the procedure, a waiting area will be allocated for patients in accordance with distance rules.

Patients who meet the Chronic Low Back and Leg Pain consensus group FBSS definition and meet the inclusion criteria will be included in the study. Before the patients are processed, data such as demographics, height, weight, which leg the pain is on, additional diseases, and medications used will be recorded. Before the procedure, patients will be evaluated with scales and methods such as Numeric Rating Scale (NRS), Oswestry Disability Index (ODI), Central Sensitization Inventory (CSI), Beck Depression Inventory (BDI), Douleur Neuropathic 4 (DN4) and a pressure algometer (baseline brand manual Quantitative sensory testing will be performed using algometer) . Those who score 40 and above on CSI will be included in Group 1 (those with CS), and those with lower scores will be included in Group 2 (those without CS). Homogeneity between groups will be ensured in terms of the surgical method applied (lumbar stabilization or microdiscectomy) and etiological cause (fibrosis and recurrent disc herniation). Patients in both groups will undergo CESI under USG guidance. Patients will be re-evaluated with NRS at 1 hour, 3 weeks and 3 months after the procedure, using the scales and methods mentioned above. A 50% or more reduction in NRS in the 3rd month will be considered treatment success.

Numeric Rating Scale (NRS) is a scale in which the patient gives a score between "0" and "10" for the back and leg pain felt, where "0" = no pain and "10" = the most severe, unbearable pain. is a scale. Turkish validity and reliability studies of the scales and surveys to be used in the study have been conducted and are stated in the references.

The Central Sensitization Inventory (CSI) includes 2 parts: part A, which evaluates symptoms thought to be related to CS, and part B, which quickly questions whether the patient has previously received a specific diagnosis. Part A contains 25 items that question the frequency of symptoms seen in SS syndromes and are scored between 0-100 points. Each symptom is defined as "never" (0 points) if the patient never experiences that symptom, "rarely" (1 point) if the patient experiences it rarely, "sometimes" (2 points) if he sometimes experiences it, "often" (3 points) if he frequently experiences it, "frequently" (3 points) if he always experiences it. It is recorded as "always" (4 points). As the patient's score increases, he or she is considered to have more symptoms related to CS.

Beck Depression Inventory (BDI) was created by Beck in 1961 to measure the characteristic attitudes and depression symptoms of patients. The survey consists of a total of 21 questions, each with four options. Each option is scored between 0-3 and the total score is calculated. In scoring, 0-9 is interpreted as normal, 10-18 as mild depression, 19-29 as moderate depression, and 30-63 as severe depression (15).

Oswestry Disability Index (ODI) consists of 10 items. Items question the severity of pain, self-care, lifting, carrying, walking, sitting, standing, sleeping, degree of pain change, travel and social life. There are 6 statements under each item, in which the patient ticks the one appropriate to his/her situation. The first statement is scored as "0" and the 6th statement is scored as "5". When the total score is calculated, it is multiplied by 2 and expressed as a percentage. The maximum score is "100" and the minimum score is "0". As the total score increases, the disability level also increases.

Quantitative Sensorial Testing (QST) is widely used in human research to investigate the contributions of the peripheral and central nervous system to pain modulation. Pressure pain threshold (PPT) measurements are also a frequently used evaluation method among QST. PPT measurements will be measured using two different regions in each patient; areas with maximum pain at the waist for group 1 (those with CS), 3 cm adjacent to the L5 spinous process (local area) for group 2 (those without CS); and the dominant hand (approximately in the middle of the proximal transverse arch) for all subjects (far pain-free area). PPT will be evaluated three times in each region, with at least 60 seconds between stimuli, and the average of these 3 evaluations will be recorded as the PPT value for this region. If patients fail to report pain to a pressure of 10 kg/cm^2, the test will be stopped and this value will be recorded as PPT.

Douleur Neuropathic 4 (DN4) is a scale that evaluates the patient's neuropathic symptoms with 4 questions. On a scale with a total score of 10, those with scores above 4 indicate the presence of neuropathic pain.

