**Previous surgery;**

**The party to be transacted; Duration of symptoms: Comorbidity:**

Radicular pain; **Previous treatments / duration :** Medications used

	Before Procedur e	1st hour	Three weeks	3 months
NRS (Waist)				
NRS (Leg)				
CSI				
BDI				

ODI				
PPT				
DN4

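### The local pressure-pain site depends on the CSI group, so its examiner cannot be masked, and nothing keeps the CSI score from the operator or the NRS collector

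*Protocol*

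**What the plan says.** All of this is in the Protocol.

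- **Group.** Section 10 lists the CSI among the pre-procedure assessments and splits patients on it: "Those who score 40 and above on CSI will be included in Group 1 (those with CS), and those with lower scores" form Group 2. The group is therefore fixed before treatment.
- **PPT.** The Quantitative Sensorial Testing paragraph of section 10 takes the local measurement at "areas with maximum pain at the waist for group 1 (those with CS), 3 cm adjacent to the L5 spinous process" for Group 2. The second site, on the dominant hand, is the same for everyone. The instrument is a manual algometer.
- **Treatment.** "Patients in both groups will undergo CESI under USG guidance". The Processing Technique section gives one procedure and one injectate for all patients. It says that an experienced algologist performs the injection, but not whether that person sees the CSI.
- **Success.** "A 50% or more reduction in NRS in the 3rd month will be considered treatment success". The patient gives the NRS score; the person who records it is not named.
- **Follow-up form.** In Annex-II, NRS (waist), NRS (leg), CSI and BDI are rows of one table whose columns run from before the procedure to 3 months.
- **Recruitment.** Section 10 requires the groups to be homogeneous in surgical method and etiology. Section D sets minimum numbers of 24 and 27.

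The text shown has no statement on masking of anyone.

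**The concern.** The study asks whether central sensitization affects the result of the injection, so its answer is a contrast between two groups defined by CSI. If the person measuring an outcome knows the group, expectation can enter that contrast. PPT is exposed because the examiner applies the pressure by hand. The NRS is the patient's own score, but it can be affected by how the question is put, and success is a cut on an integer scale. Expectations set by the operator at the injection are another possible route.

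In many observational studies the exposure cannot be hidden. Here it largely can: it is a questionnaire total, and no step of care depends on it. The written PPT rule removes that option for one outcome, and the form leaves it unprotected for the others. Bias of this kind cannot be separated from a real group difference at analysis.

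**Working it through.** **1. Who needs the group, step by step**

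| Step | Needs the group? | Does the protocol say who does it or what they see? |
|---|---|---|
| Injection | No, same for both groups | An algologist; silent on CSI |
| Local PPT | Yes, the site differs by group | Examiner not named |
| Hand PPT | No, same site for all | Examiner not named |
| NRS, including month 3 | No | Collector not named; CSI is in the same table |
| ODI, BDI, DN4 | No | Not named |
| Group counts and balance, if managed during recruitment | Yes | Not named |

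Only the local PPT row is an assessment that forces disclosure. It also means that the CSI must be scored before the baseline PPT, since the site cannot be chosen otherwise. If the same person then tests the hand, that reading is unmasked too. This is likely in practice, but the protocol does not state it.

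**2. The group sizes**

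The Power analysis section gives 21 + 25 = 46 evaluable patients, 10% loss and a total of 51. The checks are 46 × 1.1 = 50.6 and 46 / 0.9 = 51.1, so 51 is reproduced to within rounding, and 24 + 27 = 51 agrees with section D. The 21 and 25 cannot be re-derived, because no effect size or SD is given.

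**3. Sensitivity of the success comparison**

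- Baseline NRS 6: a month-3 score of 3 gives (6 − 3)/6 = 50%, a success; a score of 4 gives (6 − 4)/6 = 33%, a failure.
- Baseline NRS 4, the entry threshold: one point is 1/4 = 25% of baseline.
- One patient per group reclassified, in opposite directions, with 24 and 27: 1/24 + 1/27 = 4.2% + 3.7% = 7.9 points.
- Two per group: 2/24 + 2/27 = 15.7 points.
- One per group with the evaluable 21 and 25: 1/21 + 1/25 = 4.8% + 4.0% = 8.8 points.

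These figures show what a changed classification does to the result. They do not show that knowing the group changes any.

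**4. Illustration on a continuous score (assumed shifts)**

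Suppose there is no true difference, but knowledge of the group shifts the mean rating between groups by b SD. With 21 and 25 patients and a two-sided 5% t-test (two-sided is an assumption), the non-centrality is b / √(1/21 + 1/25) = b / 0.296 on 44 degrees of freedom.

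| Assumed b | Rejection rate with no true difference |
|---|---|
| 0.1 | 6% |
| 0.2 | 10% |
| 0.3 | 17% |
| 0.5 | 38% |

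The documents give no value of b. For scale, the same sizes detect about 0.96 SD (normal approximation) or 0.98 SD (t) with 90% power.

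**The case against.** A reader might infer that the operator and the outcome assessor are both unblinded. The documents do not support that. Nothing says that the algologist scores or sees the CSI or measures PPT, and the PPT rule binds only the person with the algometer. Success rests on a score that the patient gives, taken by someone unnamed for whom the group is irrelevant, and nothing says that this person also measures PPT.

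The form must also be read with care. It is blank, and it does not say who fills it in or in what order. In the extracted text its table breaks after the BDI row, so it cannot be shown that PPT is on the same page. NRS and CSI do stand in the same part of the table under the same time columns, which is all that is relied on here.

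A reader might also infer a bias towards a known hypothesis. The title and aims name an effect of central sensitization without a direction. That sensitized patients should do worse is a plausible expectation, but the protocol does not state it as a hypothesis.

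Finally, silence on masking in a single-centre observational study of routine care is an omission rather than a contradiction, and a common PPT site would cure the disclosure by itself. The second part holds for PPT only; the NRS would stay unprotected. The first does not reach the PPT rule, which is a written instruction. Who sees the CSI and where the algometer is placed are matters of conduct that an analysis plan could not repair.

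**Conclusion.** The point holds in limited form. Followed as written, the protocol makes it impossible to mask the examiner of local PPT. For the NRS and the injection, the protocol and form permit knowledge of the group without requiring it, although both groups are treated alike.

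No size or direction of bias can be given. The 7.9 and 15.7 points measure how fragile the success difference is, and the 6% to 38% rejection rates rest on assumed shifts of 0.1 to 0.5 SD. The conclusion also assumes that the removed pages contain no masking provision; even if they do, it could not coexist with the group-dependent PPT site.

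The change is worth making because the exposure is avoidable at small cost. The different local sites also raise a separate question of whether PPT is comparable between groups, which is not judged here.

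**What to change.** 1. In the PPT paragraph of section 10, state one local site rule that applies to every patient regardless of group.
2. Have patients complete the CSI themselves on a separate sheet, and remove the CSI row from the Annex-II visit table.
3. State in section 10 that CSI score and group are kept from the operator and from those taking NRS, PPT and DN4 until that patient's month-3 assessment is complete.
4. Name, by role, an existing team member who does not assess patients to score the CSI and to track the counts towards 24 and 27 and the balance by surgical method and etiology that section 10 requires.

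If no such person is available, adopt at least the common PPT rule and the separate CSI sheet, scored after month 3. In that case the counts and balance cannot be steered during recruitment, and the protocol should say so.

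**Cost.** A short edit to section 10 and one extra sheet, with no added visits or procedures. The assessing physician does not have the CSI total during follow-up, and someone must keep the group count separately. Whether the team has a non-assessing member cannot be seen from the text.

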## **Power analysis**

According to the study conducted by Sacaklı R. et al., based on the improvement in pain scores in the 3rd month, the number of samples was found to be 21 for the CS group and 25 for the non-CS group, with a 95% confidence interval and 90% power. Considering that 10% of the patients could not continue the study, a total of 51 patients were planned to be included.

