#### **12- CRITERIA FOR INCLUSION, EXCLUSION AND REMOVAL FROM THE RESEARCH**

##### INCLUDING:

- Being between the ages of 18-75
- Those who meet FBSS diagnostic criteria (according to CBLP)
- Radicular pain that begins at any time after surgery and persists for at least 6 months
- Those with clinically compatible epidural fibrosis and/or disc herniation at the L5 and/or S1 vertebra level on contrast-enhanced MRI
- Nrs is greater than or equal to 4
- Failure to achieve significant improvement with conservative methods

- Volunteering to participate in the study and signing a consent form

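### Local pressure pain threshold is measured at a different site in each group, so the CS versus non-CS comparison of that reading cannot be interpreted

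*Protocol*

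**What the plan says.** Section 10 (Approaches and Methods to be Applied) forms the groups from the Central Sensitization Inventory: "Those who score 40 and above on CSI will be included in Group 1 (those with CS"), and lower scores go to Group 2.

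The paragraph on quantitative sensory testing then asks for PPT in two regions per patient. The local region depends on the group: "areas with maximum pain at the waist for group 1 (those with CS), 3 cm adjacent to the L5 spinous process (local area"), where the second location applies to Group 2. The remote region, the dominant hand, is "for all subjects (far pain-free area"). Each region is tested three times and averaged, with a cap of 10 kg/cm², identically in both groups. No reason is given for the two local sites, and nothing in the protocol has both local sites measured in the same patient.

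Follow-up assessments are made "using the scales and methods mentioned above". The text does not say whether the baseline spot is re-used in Group 1. The follow-up form in Annex II, as extracted, has a single PPT row and no place for the site.

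**The concern.** The study compares patients with and without CS, and PPT is one of the measures taken in both groups. A local threshold can be compared between groups only if it is taken under the same rule in both. Here Group 1 is tested where the patient hurts most and Group 2 at a fixed anatomical landmark, so the site rule is determined completely by group.

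A spot selected because it is the most painful would be expected to have a lower threshold than a fixed landmark. That is an inference, not something the protocol states. If it is right, the site rule alone would produce an apparent local hyperalgesia in the CS group, which is the pattern a reader would attribute to CS.

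The problem arises at data collection. A statistical analysis plan cannot repair it: adjustment needs overlap between group and site rule, and there is none. More patients would make the biased difference more precise without reducing the bias.

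The rule has a side effect: the examiner must know the CSI group to choose the site. The protocol promises no blinded assessment, so no commitment is broken.

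**Working it through.** **1. The rules side by side**

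| Reading | Group 1 (CSI ≥ 40) | Group 2 (CSI < 40) | Comparable between groups? |
|---|---|---|---|
| Local PPT | Area of maximum waist pain | 3 cm from the L5 spinous process | No |
| Remote PPT | Dominant hand | Dominant hand | Yes |

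Write the expected local PPT difference (Group 1 minus Group 2) as δ + s, where δ is the effect of CS and s the effect of the site rule. The data estimate only the sum. To estimate s, some patients would have to be measured under both rules, or some patients in each group under each rule. Neither is planned.

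**2. Could a common site be used?** Yes. Patients come from "outpatient clinics with complaints of low back pain", and the L5 landmark is already used in Group 2, whose surgical procedures are meant to match those of Group 1. The entry criterion "Nrs is greater than or equal to 4" shows that all patients have pain, but not that it is in the waist, because the NRS covers back and leg. Feasibility rests on the landmark, not on the NRS.

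**3. Size, as an illustration only.** The protocol gives no PPT mean, SD or site difference, so there is no stated figure to reproduce. Assumptions: two-sided t-test at 0.05, equal SDs, δ = 0, and a site shift s in SD units. Group sizes are the planned 24 and 27 (table of volunteers) and the evaluable 21 and 25 (Power analysis: "the number of samples was found to be 21 for the CS group and 25 for the non-CS group").

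The test statistic follows a non-central t distribution with n₁ + n₂ − 2 degrees of freedom and non-centrality s / √(1/n₁ + 1/n₂).

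- 24 vs 27: √(1/24 + 1/27) = 0.281; for s = 0.5 the non-centrality is 0.5/0.281 = 1.78.
- 21 vs 25: √(1/21 + 1/25) = 0.296; for s = 0.5 it is 0.5/0.296 = 1.69.

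Probability of a falsely significant local PPT difference:

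| Assumed site shift | 24 vs 27 | 21 vs 25 |
|---|---|---|
| 0 | 5.0% | 5.0% |
| 0.25 SD | 14.1% | 13.1% |
| 0.50 SD | 41.6% | 37.9% |
| 0.75 SD | 74.6% | 69.8% |

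The error rate reaches 10%, twice nominal, at a shift of 0.187 SD (24 vs 27) or 0.197 SD (21 vs 25).

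**4. Partial overlap.** Inclusion requires pathology at L5 and/or S1, so the painful area may often lie near the L5 point. Suppose each Group 1 patient has a 50% chance of no shift at all (100,000 simulated trials):

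| Shift in the others | 24 vs 27 | 21 vs 25 |
|---|---|---|
| 0.25 SD | 7.2% | 6.9% |
| 0.50 SD | 13.8% | 12.9% |
| 0.75 SD | 24.8% | 22.3% |

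Overlap weakens the bias without removing it.

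**5. Change from baseline.** If the Group 1 spot is re-used, a constant site offset cancels within each patient. If the spot is chosen afresh at each visit, the Group 1 change also contains a change of site, which Group 2 does not have. The protocol does not say which applies.

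**The case against.** The strongest reply is that the threatened comparison is not written down. The protocol specifies no between-group test of local PPT, the aims do not mention PPT, and the success criterion ("A 50% or more reduction in NRS in the 3rd month will be considered treatment success") and the sample size rest on pain scores. This is correct, and the comparison should be described as implied. It is nevertheless strongly implied: PPT is collected in both groups of a study built on that contrast, and section 10 introduces sensory testing as a way to study peripheral and central contributions to pain.

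Second, full confounding applies to the site rule, not necessarily to the physical location, because the painful area may coincide with the L5 point in some patients. This also stands, and the partial-overlap figures allow for it. But unless the site is recorded, the extent of overlap cannot be established afterwards.

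Third, the direction of the bias and the sizes of the shifts are assumed. That is so. The percentages show how a test responds to a shift of a given size and say nothing about the shift in this trial. The inability to separate CS from site does not depend on them.

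Fourth, the single PPT row is a minor matter: the text already calls for one value per region, one row can hold two values, and the form may have suffered in extraction. The point about the form is secondary.

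Finally, the wording may be a product of translation. It is still the operative text, and it names both groups with different sites.

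**Conclusion.** The concern holds. Followed as written, the protocol yields local PPT levels that cannot be compared between the CS and non-CS groups, because the measurement site changes with the group. This follows from the text alone and needs no assumption. How large the distortion is, and that it favours an apparent CS effect, are assumptions; an average shift of only about 0.19 to 0.20 SD would already double the false-positive rate.

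The reach is limited to one of the two PPT readings. Dominant-hand PPT remains comparable, and treatment success, CSI grouping and sample size do not use PPT. The point should be fixed, but it does not threaten the main result.

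**What to change.** Replace the group-dependent rule in section 10 with one local site for every patient at every visit, for example 3 cm lateral to the L5 spinous process on the symptomatic side, with a stated convention for bilateral symptoms. With the same rule in both groups, s = 0 and the false-positive rate returns to 5%. The examiner then no longer needs to know the CSI group to choose the site.

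If the most painful point is also of interest, measure it in both groups as an additional site, record its position, and re-use that position at 3 weeks and 3 months.

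On the Annex II form, split the PPT row into local site and hand.

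Cost: one sentence in the protocol and one row on the form. No extra patients or equipment are needed, and no extra test unless the optional second local site is added. The change has to be made before measurements are taken, because readings already collected under the present rule cannot be corrected by analysis.
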